17.1.6.2. Observed Data Only

This analysis will be performed using the mFAS. No imputation for missing data will be performed.

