Longitudinal continuous endpoints will also be analyzed up to Week 24 using a linear mixed effects model. The model will include treatment group, visit, interaction of treatment-by-visit, and randomization stratification factors as factors and Baseline measure value as covariates. An unstructured covariance matrix will be specified for the within-subject measurements. LS means and LS mean differences between treatment group with unadjusted p-values and corresponding 95% CIs will be reported at each scheduled visit.

No hypothesis tests between treatment groups will be performed for endpoints measured during the Extension Treatment Period. Only descriptive statistics will be provided.

Continuous variables will be summarized using the number of observations, mean, SD, median, minimum, and maximum. Categorical variables will be summarized using frequency counts and percentages.

Subjects receiving any rescue therapy will have efficacy assessments after rescue therapy set to missing (continuous variable) or considered as treatment failures/non-responders at subsequent timepoints (dichotomous variables). Details and handling of rescue therapy for analysis will be contained in the protocol and SAP.

Safety Analysis:

All safety data will be listed and summarized by treatment group. All treatment-emergent AEs (TEAEs) will be coded using the Medical Dictionary for Regulatory Activities (MedDRA) and tabulated by System Organ Class and Preferred Term. Incidence of AEs, serious adverse events, adverse events of special interest, and AEs leading to study treatment discontinuation will be summarized and presented in descending order of frequency. In addition, details regarding risk-based safety analyses (eg, risk difference, hazard ratio) and exposure adjusted incidence rates will be described in the SAP. Laboratory parameters will be summarized by treatment group at each scheduled assessment timepoint using descriptive statistics.

Associated laboratory parameters such as hepatic enzymes, renal function, and hematology values will be grouped and presented together. Individual subject values will be listed and values outside of the standard reference range will be noted. Shift tables and analyses of changes from Baseline will be produced. The change from Baseline for each of the vital signs and ECG parameters will be summarized. Incidence of abnormal vital signs parameters and outlier ECG results will be tabulated.

Pharmacokinetic Analysis:

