11.4.2. Sensitivity Analyses

In addition to the primary method for handling missing data and rescue medication/rescue procedure use in the FAS described in Section 11.4.1, the following sensitivity analyses will be performed for primary, secondary, and selected CCI using alternative methods to handle missing data and/or in alternative analysis populations:

- MI usually assumes that the data are missing at random (MAR) but MAR cannot be verified using the observed data. Therefore, the sensitivity of inferences to departures from the MAR assumption will be examined. For the MI analysis of the primary endpoint of percent change from Baseline in esophageal PEC at Week 16 and Week 24, data MAR within each treatment group will be investigated using tipping point analyses method and results will be described using Rubin’s rule [1]
- Percent change in esophageal PEC from Baseline to Week 16 and Week 24 will be analyzed in the modified Full Analysis Set (mFAS), data will be set to missing after rescue medication/rescue procedure uses
- Proportion of subjects with esophageal PEC of < 15 and ≤ 6 eos/hpf at Week 16 and Week 24 will be analyzed in the FAS using PEC imputed by the MI method discussed in Section 11.4.1
- Proportion of subjects with esophageal PEC of < 15 and ≤ 6 eos/hpf at Week 16 and Week 24 will be analyzed in the mFAS using PEC imputed by the MI method discussed in Section 11.4.1
- Observed data analyses in mFAS, regardless of rescue medication/rescue procedure use and without missing data imputation:
 - For longitudinal continuous variables, a linear mixed effects model will be performed and results will be reported by visit.
 - For longitudinal dichotomous measures, logistic regression analysis may be performed by visit
- Completers analyses (also known as complete case) of primary and secondary endpoints for subjects who complete 16 and 24 weeks of study treatment

- Per Protocol Set analyses in subjects who meet the criteria of Per Protocol definition approved prior to database lock

Detailed sensitivity analysis methods will be described in the SAP.

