8.3. MISSING DATA

Missing adverse event (AE) relationship to study drug and AE seriousness will be imputed as described in Section 17.1.1.2 and 17.1.3, respectively. Partial or missing AE start dates, Concomitant Medication (CM) start dates, and hospitalization dates will also be imputed as described in Appendix 2. No other missing safety data will be imputed.

Missing efficacy data will be handled as described in Sections 16.1.2, 16.2.2, and 16.3.2. In the primary analysis of the primary endpoint, PEC after rescue medication and/or rescue procedure uses will be set to missing; all missing data will then be imputed in the FAS using multiple imputation. In the main analyses of all binary responder-type endpoints, all subjects with missing data, regardless of reason for missingness, will be considered as nonresponders. In the main analysis of continuous or score endpoints, subjects with missing data will be handled using observed cases only, multiple imputation, or a linear mixed effect model.

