17.1.2. MISSING DATA METHODS FOR PRIMARY EFFICACY VARIABLE

Subjects who 1) discontinue the study for worsening of disease, lack of efficacy, or adverse event related to EoE, 2) use a rescue medication for EoE, or 3) have rescue medical procedure during the study as confirmed after blinded review by clinical and medical team members before study unblinding will be considered to have a missing outcome in the analysis of all efficacy endpoints at any subsequent timepoints, including the primary endpoint. The rescue medications/rescue medical procedure will be identified by the Pfizer clinical team during blinded data review. The detailed information regarding the identification of rescue therapy is provided in Appendix 4. In scenarios 2 and 3 above, if a subject has an efficacy measurement collected after the initiation of rescue medication/rescue medical procedure, the observed data will be censored at the time of initiation and they will be considered as having a missing outcome. Subjects in all 3 scenarios above may still be included in the respective Per Protocol Set, provided they do not violate other criteria for Per Protocol Set. For example, they will be excluded from the respective Per Protocol Set if they initiate a prohibited medication before the Week 16 efficacy assessment that can affect efficacy of the study treatment and the indication is unrelated to EoE.

Analysis visits will be mapped as per Section 6.4 before any missing data imputation method is applied.

Subjects who initiate rescue medication will have PEC results after the start of rescue medication/rescue medical procedure set to missing. All missing PEC at Week 16 and Week 24 will then be imputed using multiple imputation under missing at random (MAR) procedure with a fully conditional specification (FCS) and predictive mean

matching for PEC as the primary missing data method. There are two different types of missing data patterns: non-monotone and monotone. A subject with missing data at any post-Baseline visit, and a non-missing data point after that visit is said to have intermittent missing data (non-monotone). A subject with missing data at any post-Baseline visit and at all subsequent visits is said to have monotone missing data.

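### Does SAP 17.1.6.2 leave open whether the observed-data check on percent change in PEC keeps values measured after rescue?

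*SAP*

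**What the plan says.** Protocol 11.4.2 lists two mFAS analyses that bear on percent change in PEC.

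- In the first, percent change in PEC at Weeks 16 and 24 "will be analyzed in the modified Full Analysis Set (mFAS), data will be set to missing after rescue medication/rescue procedure uses".
- The second is headed "Observed data analyses in mFAS, regardless of rescue medication/rescue procedure use and without missing data imputation". Its model is given as well: "For longitudinal continuous variables, a linear mixed effects model will be performed and results will be reported by visit".

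The Protocol Synopsis has a general rule that continuous assessments after rescue are set to missing, so the wording of the second item is what exempts it.

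The whole of SAP 17.1.6.2 (Observed Data Only) reads: "This analysis will be performed using the mFAS. No imputation for missing data will be performed". It mentions neither rescue nor a model.

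SAP 17.1.2 says that subjects who use rescue "will be considered to have a missing outcome in the analysis of all efficacy endpoints at any subsequent timepoints, including the primary endpoint". For values collected after rescue starts, it adds that "the observed data will be censored at the time of initiation and they will be considered as having a missing outcome". It names no exception.

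SAP 8.3 puts the rule more narrowly: "In the primary analysis of the primary endpoint, PEC after rescue medication and/or rescue procedure uses will be set to missing". SAP 3.3 declares no change from the protocol's analyses.

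**The concern.** Both protocol items use the mFAS, so two sentences that name only the mFAS and the absence of imputation could be taken to implement either one. SAP 17.1.2 covers all efficacy endpoints. Applied literally, it would strip post-rescue values from 17.1.6.2 and leave a complete-case analysis of censored data.

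The observed-data item is the only sensitivity analysis in the protocol stated to use PEC measured after rescue. The tipping-point analysis shifts imputed values, and the responder analyses count rescue as failure. If the values were dropped, no visible SAP analysis of the primary endpoint would show what happens when they are kept, and SAP 3.3 would not have declared the loss.

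Two further points seem to deepen the gap. The Planned Analyses by Endpoint table has no column for the observed-data analysis. SAP 2.4 promises a supplementary mFAS analysis, but SAP 17.1.5 lists only the Completers and Per Protocol Sets.

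**Working it through.** **1. Which protocol item does SAP 17.1.6.2 implement?**

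| Feature | Protocol: as-observed item | Protocol: censored mFAS item | SAP 17.1.6.2 |
|---|---|---|---|
| Label | Observed data | none | Observed Data Only |
| Set | mFAS | mFAS | mFAS |
| Imputation | none | not stated | none |
| Post-rescue values | kept | set to missing | not stated |
| Model | linear mixed effects, by visit | not stated | not stated |

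Label, set and imputation rule all agree with the as-observed item. Only the set agrees with the other by its stated terms.

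**2. What else in the SAP bears on it?**

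- 17.1.2 presents multiple imputation after censoring as the primary missing-data method. 17.1.3 then lists the tipping-point and observed-data approaches as additional methods.
- 17.1.6 introduces its subsections as explorations of different missing-data approaches.
- 8.3 ties the censoring of PEC to the primary analysis.
- The Planned Analyses table attaches censoring to individual analyses through footnotes c, d and e. That would be largely redundant if 17.1.2 governed every analysis.
- 3.3 declares no departure, so protocol 11.4.2 stands.

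For the model, protocol 11.5 gives the terms: treatment, visit, their interaction, stratification factors and baseline, with unstructured covariance.

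**3. Who is affected at Week 16?** Only subjects rescued before the Week 16 biopsy who have no earlier biopsy in the Week 16 window.

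- SAP Appendix 4 does not count therapy begun on or after the last dose as rescue, so the readings differ mainly for subjects rescued while on study drug.
- Protocol 9.6 asks for the early termination visit before any new treatment. SAP 6.4 lets that visit fill the Week 16 window (Days 100 to 127), so a pre-rescue biopsy can still count.
- The option in protocol 6.7.4 to stay in the study on rescue covers Weeks 16 to 24.

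**4. How far could one value move the result?** Planned arms: 96 × 3/8 = 36 for each etrasimod dose and 96 × 2/8 = 24 for placebo. Assume all are in the mFAS. The factor for a difference of means is √(1/24 + 1/36) = 0.2635.

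*Percent-change scale (the scale of the protocol's model).* Let m be the mean of the other 23 placebo subjects. Keeping one value at the -100% floor moves the placebo mean by (100 + m)/24.

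- m = 0: 100/24 = 4.17 points.
- m = -40: 60/24 = 2.5 points.
- SE = SD × 0.2635: 13.2 for SD 50 and 26.4 for SD 100.
- Ratios: 2.5/26.4 = 0.09 to 4.17/13.2 = 0.32 SE.

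Both m and SD are assumptions. A worsening value has no fixed limit.

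*Rank scale (if the primary model were reused).* SE = √((96² − 1)/12) × 0.2635 = 27.71 × 0.2635 = 7.30, ignoring ties and covariates. One placebo value at rank 1 moves the mean-rank difference by p/24, where p is the mean rank of the other 23 among 95.

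- p = 48 (centred): 2.0 ranks, 0.27 SE.
- p = 84 (extreme): 3.5 ranks, 0.48 SE.

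**5. Illustration over rescue rates.** This simulation of 2 mg versus placebo used 4,000 trials per row, and every input is assumed. The log PEC ratio has mean -0.1 on placebo and -0.7 on 2 mg, SD 0.8. The poorest responders are rescued, and rescue lowers log PEC by 1.5.

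| Rescue, placebo / 2 mg | Expected values at stake | Median difference, keep | Median difference, drop | Gap |
|---|---|---|---|---|
| 5% / 2% | 1.2 / 0.72 | -37.6 | -38.3 | 0.7 |
| 10% / 5% | 2.4 / 1.8 | -33.8 | -36.0 | 2.2 |
| 20% / 10% | 4.8 / 3.6 | -25.2 | -29.9 | 4.7 |

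The two readings are different analyses, but they stay close unless rescue is common.

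**The case for a change.** The strongest counter-argument is that 17.1.2 is explicit and unqualified, while the as-observed reading of 17.1.6.2 is inferred from a title, a declaration of no change and neighbouring sections. A programmer working from the SAP alone could apply 17.1.2 throughout. Section 17.1.3 does not help, since its pointer for details uses an outdated section number. Post-rescue biopsies can plainly exist: Appendix 4 judges some therapies by how long they had been used at the time of the endoscopy.

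What stands is that the SAP text is incomplete on rescue handling and model. It does not follow that the analysis is undefined. The protocol is the parent document, answers both questions in so many words, and is said by the SAP itself to be unchanged. The literal reading requires the analyst to overlook that.

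The mFAS mismatch between SAP 2.4 and 17.1.5 is weaker still. SAP 2.4 does not say how its mFAS analysis treats rescue, and 17.1.6.2 already supplies an mFAS analysis under the sensitivity heading, which is where the protocol also files its mFAS items. At most, the censored mFAS item of protocol 11.4.2 is not listed again in SAP 17.1.

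**Conclusion.** This is a drafting gap that analysts fill sensibly from the documents they hold, and it calls for no change to the plan. Post-rescue PEC is kept in the observed-data analysis and the model is linear mixed effects by visit, because protocol 11.4.2 says so and SAP 3.3 declares no departure.

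The reach is one sensitivity analysis, and mainly subjects rescued on study drug with no earlier biopsy in the Week 16 window. The documents give no rescue rate, so the actual effect cannot be determined. The figures of 0.09 to 0.32 SE per placebo value on the percent-change scale, and 0.27 to 0.48 SE on ranks, rest on extreme values, assumed means and SDs, and all 96 subjects being in the mFAS.

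The primary analysis is unambiguous: post-rescue PEC is set to missing and then multiply imputed. P-values are unadjusted, with no type I error control (SAP 8.4), so no formal testing sequence depends on this check. The output shells are in a separate file (SAP 1), and the text of SAP 17.2.4 and 17.2.5 is not visible; neither is counted as missing here.

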17.2. SECONDARY EFFICACY

The secondary efficacy analyses will be performed for the FAS.

17.2.1. SECONDARY EFFICACY VARIABLES & DERIVATIONS

The secondary efficacy analyses will be performed for the FAS. The secondary efficacy endpoints are:

- Change from Baseline in DSQ total score at Week 16
- Change from Baseline in Esophageal PEC at Week 16.
- Proportion of Subjects with Esophageal PEC < 15 eos/hpf at Week 16
- Proportion of Subjects with Esophageal PEC \leq 6 eos/hpf at Week 16

Change from Baseline in DSQ total score at Week 16 will be based on daily DSQ score from subject daily Diary data. The DSQ total score and daily DSQ score calculations are provided below. An increase in DSQ total score indicates worsening of dysphagia symptoms.

Calculation Approach	DSQ Total Score	Daily DSQ Score
14-day period approach ^a	
DSQ total Score = (Sum of daily DSQ score with 14-day period preceding the scheduled visit day) \times 14 / (Number of days with diaries reported with nonmissing data within 14-day period).
 
Shifting rule when calculating DSQ total score at each visit based on the number of reported diary entries within the 14-day period prior to the visit:
 
Baseline visit :
 
If there are less than 8 reported diaries that are available within the 14-day period prior to baseline, then the most recent 8 reported diaries in a consecutive 14-day period would be used to calculate the DSQ total core. In order to determine the most recent 14-day period with the minimum number of reported diaries, it may be necessary to make adjustments in some cases by shifting to earlier diary entries. Such 14-day periods cannot be shifted for more than 7 days (not including the study visit day). After shifting 7 days, if there are still less than 8 reported diaries
	
Daily DSQ Score= sum of answers to Questions 2 and 3 in the daily DSQ questionnaire
 
Daily DSQ Score is set to missing if the diary is not reported or if the diary is reported but the answer to Question 1 is “No” in daily DSQ questionnaire. In this case the diary is considered as missing
 
Daily DSQ Score is set to zero if the answer to Question 2 is “No” in daily DSQ questionnaire

	
within the 14-day period, then the DSQ total score for baseline visit will be set to missing.
 
Week 2 visit: If there are less than 8 reported post-baseline diaries are available within the 14-day period prior to week 2 visit, then DSQ total score will be set to missing without any shift rule applied.
 
All other post baseline visits after Week 2: If there are less than 8 reported diaries that are available within the 14-day period prior to baseline, then the most recent 8 reported diaries in a consecutive 14-day period would be used to calculate the DSQ total score. In order to determine the most recent 14-day period with the minimum number of reported diaries, it may be necessary to make adjustments in some cases by shifting to earlier diary entries. Such 14-day periods cannot be shifted for more than 14 days (not including the study visit day). After shifting 14 days, if there are still less than 8 reported diaries within the 14-day period, then the DSQ total score for baseline visit will be set to missing.
 
The DSQ total score range is 0 to 84
	

14-day period: worst case scenario approach^b
	
DSQ total score calculation: same as 14-day period approach
 
Shifting rule: same as as 14-day period approach
 
The DSQ total score range is 0 to 84
	
Daily DSQ Score= sum of answers to Questions 2 and 3 in the daily DSQ questionnaire
 
Missing Daily DSQ Score handling approach is the same as 14-day approach except that: Daily DSQ Score is set to (maximum value of) 6 if the answer to Question 1 is “No” in daily DSQ questionnaire and the answer for Food Avoidance Question (FAQ) is “Because of eosinophilic

		
esophagitis symptoms”
 
Daily DSQ Score is set to zero if the answer to Question 2 is “No” in daily DSQ questionnaire


7-day period approach^b
	
DSQ total Score = (Sum of daily DSQ score with 7-day period preceding the scheduled visit day) ×7 / (Number of days with diaries reported with nonmissing* data within 7-day period).
 
Shifting rule when calculating DSQ total score at each visit based on the number of reported diary entries within the 7-day period prior to the visit:
 
Baseline visit and each post baseline visit: If there are less than 4 reported diary entries that are available within the 7-day period prior to the visit, then the most recent 4 reported diary entries in a consecutive 7-day period would be used to calculate the DSQ total score. In order to determine the most recent 7-day period with the minimum number of reported diaries, it may be necessary to make adjustments in some cases by shifting to earlier diary entries. Such 7-day periods cannot be shifted for more than 7 days (not including the study visit day). After shifting 7 days, if there are still less than 4 reported diary entries within the 7-day period, then the DSQ total score for baseline visit will be set to missing.
 
The DSQ total score range is 0 to 42
	
Same as 14-day period approach

^a Primary approach to calculate DSQ total score

^s Sensitivity approach to calculate DSQ total score

Change from Baseline in esophageal PEC at Week 16 will be based on the central EGD results.

Proportion of subjects with esophageal PEC < 15 eos/hpf and ≤ 6 eos/hpf at Week 16, will be based on central reading of the EGD results. Subjects who achieve esophageal PEC < 15 eos/hpf and ≤ 6 eos/hpf will be referred to as responders, respectively. Subjects who do not achieve esophageal PEC < 15 eos/hpf and ≤ 6 eos/hpf will be referred to as nonresponders, respectively.

Planned Analyses by Endpoint

Endpoint (at Week 16)	ANCOVA ^a / Weighted MH	Sensitivity Analyses: MI	Sensitivity Analyses: Tipping Point Analysis	Completer Sets and Per Protocol Set	Linear mixed effects model
Key primary endpoints					
Percent Change from baseline in esophageal PEC	X ^c	X ^e	X ^c	X ^c	
Key secondary endpoints					
Change from baseline in DSQ total score		X ^{e, f}	X ^{e, f}	X ^{e, f}	X ^{b, f, g}
Change from baseline in esophageal PEC	X ^c	X ^e	X ^c	X ^c	
Proportion esophageal PEC < 15 eos/hpf	X ^d	X ^e		X ^d	
Proportion esophageal PEC ≤ 6 eos/hpf	X ^d	X ^e		X ^d	

^a No rank transformation will be applied

^b No missing data methods will be implemented since missing data will be handled in the linear mixed effect model.

^c Subjects who initiate rescue medication/rescue procedure will have assessments collected after the rescue medication/rescue procedure is initiated set to missing.

^d Subjects who initiate rescue medication/rescue procedure will have assessments collected after the rescue medication/rescue procedure is initiated set to missing. Missing data for any reason will be considered as nonresponder. Adjusted difference and p-values are based on the estimated common risk difference using the MH weights

^e Subjects who initiate rescue medication/rescue procedure will have assessments collected after the rescue medication is initiated set to missing. Missing data will be imputed using multiple imputation.

^f primary approach (14-day period approach) will be used to calculate DSQ total score

^g sensitivity approaches (14-day period: worst case scenario approach and 7-day period approach) will be used to calculate DSQ total score.

In addition, some of the additional analyses above will be conducted as follows:

Percent change from baseline in esophageal PEC at Week 16 above will be repeated at week 24 using the same ANCOVA model.

Change from baseline in DSQ total score at Week 16 above will be repeated for week 2, 4, 6, 8, 10, 12, 14, 20 and 24 in Double-Blind Treatment Period, using the same linear mixed effects model for change from baseline in DSQ total score at Week 16.

